8.4. Protective Efficacy

In order to determine Protective Efficacy over time, the tests will continue every hour as described in section 8.3 until at least 50% of midges are probing or biting compared with control (i.e. 50% Protective Efficacy), or until 12 hours post application.

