
Exclusion Criteria:
	
 • Suspected or known to be sensitive or allergic to midge bites; • Participated in an interventional study (other than a biting insect challenge study) in the previous 3 months; • Participated in a biting insect challenge study in the previous 72 hours; • Aware of having any cardiovascular or respiratory disorder (whether active or inactive) (e.g. asthma); • Individuals with localized skin disorders affecting the forearm; • Allergic to any of the test product ingredients; • Extensive tattooing or other conditions of the forearm which would make interpretation of the bite test results difficult; • Women who are pregnant, nursing or intending to become pregnant; • Previous anaphylaxis; • Aware of having a compromised immune system;(an immune system that is temporarily or permanently incapable of working at full capacity); • Phobia of flying insects; • Travelled to a mosquito-borne disease endemic area in the last 3 months.

Efficacy Endpoint(s):
	
Primary: Median Complete Protection Time for the repellent products, tested against Culicoides nubeculosus midges.
 
Secondary: Percentage protective efficacy of the repellent products, tested against Culicoides nubeculosus midges.

Safety Endpoint(s):
	
Adverse event data will be collected and summarised.

Statistical Methods:
	
Median Complete Protection Time will be calculated using the Kaplan Meier survival-function.
 
Two-way analysis of variance followed by Tukey's tests or general linear mode will be used to compare the mean complete-protection time for the tested repellents

Investigation Site(s):
	
Single-centre: Arthropod Control Product Test Centre (arctec), Chariot Innovations Limited, a wholly-owned subsidiary of the London School of Hygiene & Tropical Medicine (LSHTM).

TABLE OF CONTENTS

1. INTRODUCTION.....	7
2. OBJECTIVES.....	7
3. STUDY DESIGN	7
3.1. STUDY ENDPOINTS.....	8
3.2. RISKS AND BENEFITS	8
3.2.1. Midges	8
3.2.2. Product	8
4. PARTICIPANT ENTRY	9
4.1. SCREENING PROCEDURES	9
4.2. INCLUSION CRITERIA	9
4.3. EXCLUSION CRITERIA	10
4.4. WITHDRAWAL CRITERIA.....	10
5. RANDOMISATION AND ENROLMENT	11
6. TREATMENTS	11
7. SAFETY REPORTING FOR NON-DRUG TRIALS.....	12
7.1. DEFINITIONS	12
7.2. REPORTING PROCEDURES	12
7.2.1. Non serious AEs	12
7.2.2. Serious AEs	12
8. TEST METHODOLOGY.....	13

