APPENDIX 3: FLOWCHART FOR SAFETY REPORTING24

APPENDIX 4: SAMPLE SIZE CALCULATION FOR A COMPARISON TRIAL BETWEEN A POSITIVE CONTROL AND TWO MIDGE REPELLENT PRODUCTS.....25

1. Introduction

Mosquitoes, midges and other biting insects are vectors of extremely important diseases such as malaria, yellow fever, filariasis and many viruses and also may be of great nuisance value. The use of repellent products can provide added personal protection from disease transmission and nuisance bites. New effective repellents would offer an additional option for protection against biting insects. The tests carried out by *arctec* provide important information on the effectiveness of skin repellents, which will be used for label claims to accurately inform consumers and registration purposes.

The aim of this study is to determine the effectiveness of two topically applied insect repellent products provided by NEO-INNOVA HEALTHCARE LIMITED and one positive control containing the UK repellent brand 'Smidge'.

2. Objectives

Primary objective: To determine and compare the median complete protection time (CPT) of two insect repellent products and a positive control against *Culicoides nubeculosus* (midges).

Secondary objective: To determine and compare the protective efficacy of two insect repellent products and a positive control against *Culicoides nubeculosus* (midges).

3. Study Design

This is a single-centre, single-arm study with all participants testing two formulations containing PMD and a positive control product containing Picaridin. The control for each test is an untreated arm. There is no blinding or randomisation employed, since the outcome measures are based on midge behaviour. Repellent product testing takes place in a laboratory setting using 7 participants (preferably gender balanced). Each participant will test both PMD formulations and a positive control product (see section 8).

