3.1. Study Endpoints

The primary endpoint is the median Complete Protection Time (CPT) of the repellent products. The CPT is defined as the time between application of the repellent product and the occurrence of the first probe or bite in a 1 minute test, followed by a confirmatory probe or bite within 30 minutes.

The secondary endpoint is an assessment of the products Protective Efficacy (PE) over time. Protective Efficacy over time will be expressed as the percentage of midges probing or biting at hourly intervals from the time of the repellent application to the end of the test (when 50% or more midges are probing or biting the test arm vs. untreated control, or 12 hours).

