9.2. Data analysis

The endpoint for Complete Protection Time will be time to treatment failure for each participant test. Treatment failure is the time at which the product no longer provides complete protection, which is determined as the time at which one probe or bite occurs in a 1 minute test, followed by a confirmatory probe or bite within 30 minutes. Using IBM SPSS Statistics 20, the times to treatment failure will be analysed using Kaplan-Meier Survival functions, and from these the median Complete Protection time and 95% confidence intervals will be calculated.

A linear regression will be used to compare the mean complete-protection time for the tested repellents. As a sensitivity analysis we will use linear regression to estimate the mean CPT difference between groups, but we will generate robust standard errors by relaxing the assumption of independence of observations between the same participant within the study, allowing for correlation between observations from the same participant in the variance-covariance matrix.

The Protective Efficacy over time from application will be calculated using the formula below at each hour and presented as a summary table and graph. Using IBM SPSS Statistics 20, the PE will be analysed using a two-way analysis of variance followed by Tukey's tests or generalised linear model.

$$PE = \frac{\text{Midges probing on control} - \text{Midges probing on treatment}}{\text{Midges probing on control}} \times 100$$

Adverse Events will be tabulated and included in the study report. Adverse events occurring after the end of participant participation but before the end of the study will be listed separately.

10. Safety and Data Monitoring

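### Section 9.2 compares hourly Protective Efficacy without naming the factors or unit of analysis, and has no rule for hours after a test stops at 50% PE

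*Combined protocol and SAP*

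**What the plan says.** The secondary objective (Section 2) is "To determine and compare the protective efficacy of two insect repellent products and a positive control", and the synopsis names the endpoint as "Percentage protective efficacy of the repellent products". By Section 3, "Each participant will test both PMD formulations and a positive control product", so each of the 7 participants contributes three tests.

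Section 3.1 follows PE hourly "to the end of the test (when 50% or more midges are probing or biting the test arm vs. untreated control, or 12 hours"). Section 8.4 gives the same rule: readings go on "until at least 50% of midges are probing or biting compared with control (i.e. 50% Protective Efficacy), or until 12 hours post application".

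Under Section 9.2, PE "will be calculated using the formula below at each hour and presented as a summary table and graph", and then "the PE will be analysed using a two-way analysis of variance followed by Tukey's tests or generalised linear model". Factors, unit of analysis, error term and handling of hours after a stop are not stated. Section 9.2 does make one allowance for repeated observations, "allowing for correlation between observations from the same participant in the variance-covariance matrix", but only in the sensitivity analysis of Complete Protection Time (CPT). Section 4.4 says that data up to a withdrawal are used. Section 10.2 describes tests halted for an adverse event. Neither says how such a test enters the PE analysis, or separates it from a test that ended because PE reached 50%.

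**The concern.** There are two distinct difficulties.

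(a) **Selection at late hours.** The stop depends on the outcome. Once the first test has stopped, an hourly mean of the readings taken describes only the better-performing tests. It is too high for the product as a whole, and more so for a product that fails sooner, so a true difference between products is reduced.

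(b) **Unit of analysis.** Hourly readings within a test share one participant, one application and one day. If they are pooled as independent rows, the product comparison is judged against the wrong error term. This happens whether or not any test stops early.

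The PE comparison is the whole of the secondary objective, and Section 3.2.2 says that the results will inform labelling. An analyst who settles the layout and the post-stop handling after seeing the data could reach materially different answers.

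**Working it through.** **1. The stop expressed as PE.** With C and T the control-arm and treated-arm counts, Section 9.2 gives PE = 100 × (C − T)/C = 100 × (1 − T/C). A ratio T/C of at least 0.5 therefore means PE of 50% or lower.

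**2. Rows against tests.** 7 participants × 3 products = 21 tests. Hours 0 to 12 give up to 13 readings each, so 21 × 13 = 273 rows. Product-and-hour ANOVA on complete rows has 273 − 1 − 2 − 12 = 258 error degrees of freedom. With one value per test and factors participant and product, there are (7 − 1) × (3 − 1) = 12.

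**3. The plan's own figure, and a spread to borrow.** The documents state no sample size, power or spread for PE. Appendix 4 gives n = 7 for CPT from n = 2σ²f/δ², with δ = 120 min, 80% power and α = 0.05/2, but does not state σ. Here f = (2.2414 + 0.8416)² = 9.505. With σ = 68.9 min, n = 2 × 68.9² × 9.505/120² = 6.27, rounded up to 7. That σ reproduces all 30 cells of the two Appendix 4 tables. In hours it is about 69/60 = 1.15. This is the spread of a different quantity, used only for want of a better one.

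**4. Assumptions (none from the documents).** PE declines logistically with scale 1 h. The half-time (when PE reaches 50%) varies between tests with SD 1.15 h. On average 20 control midges probe (40% of 50), redrawn if below 10. Testing stops at the first observed PE of 50% or lower.

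**5. Late-hour means, half-time 6 h.** The last column is what all tests would have shown had testing continued.

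| Hour | Tests running of 7 | Mean PE, running | Mean PE, all |
|---|---|---|---|
| 6 | 5.3 | 57 | 48 |
| 7 | 3.3 | 45 | 29 |
| 8 | 1.4 | 35 | 14 |

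As a consistency check at hour 7, the stopped tests would average (7 × 29 − 3.3 × 45)/(7 − 3.3) = 54.5/3.7, or about 15, well below the 45 on display.

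Varying the assumptions:
- SD 0.5 h: 50/31/18 against 48/26/10.
- SD 2 h: 66/58/52 against 48/33/20.
- Half-time 13 h: only 71 against 68 at hour 12.
- Half-time 16 h: no bias.

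A second simulation (half-time 8 h, slope 0.6 per hour, participant and test SDs of 1 h each) gave 57 against 47 at hour 8 and 41 against 22 at hour 10.

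**6. Effect on a true difference (half-times 6 and 8 h).** Mean PE over hours 0 to 12 differs by 15.8 points in all tests. A product-and-hour model on the stopped readings gives 12.3, a loss of 3.5/15.8 = 22%. A repeat gave 11.7 to 12.0 against about 15.6, a loss of 23 to 25%. The second simulation's average difference fell from 15.1 to 11.5 (24%), and from 14.4 to 9.6 (33%) with participant SD 2 h.

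**7. False-positive rate, three identical products, nominal 5%, product and hour on pooled readings.** Columns give the share of half-time variance due to participants.

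| Half-time | 0% | 30% | 60% | 95% |
|---|---|---|---|---|
| 6 h | 31% | 20% | 8% | 0.3% |
| 13 h | 28% | 19% | 8% | 0.4% |
| 16 h | 11% | 8% | 6% | 2% |

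- Participant and product on pooled readings, no hour term: 0% for half-times of 6 to 10 h, with 0.1% power for half-times 6/6/8 h.
- Product, hour and participant (second simulation): 13 to 41% when test SD is at least 1 h.
- Product and hour with no stopping at all (second simulation): still 14 to 52% when test SD is at least 1 h.

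**8. One value per test, participant and product.** Error was 2.5 to 5.4% with zero entered after the stop and 2.5 to 5.0% with the last value carried forward. The second simulation gave 4.4 to 5.5% and 4.1 to 5.1% where tests stop before 12 h, and about 3.5% at a 16 h half-time. Overall power at a 30% participant share, beside a plain per-test average of the readings taken:

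| Half-times (h) | Zero | Carried forward | Readings taken only |
|---|---|---|---|
| 6/6/8 | 91% | 52% | 30% |
| 10/10/12 | 90% | 87% | 59% |
| 12/12/14 | 71% | 78% | 82% |
| 13/13/16 | 72% | 80% | 88% |

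**The case against.** **The layout is unspecified, not shown to be wrong.** A reader might infer that the PE model omits a participant term. The documents do not establish that, because Section 9.2 names no factors. The synopsis applies nearly the same ANOVA and Tukey wording to CPT, which has one value per test, so participant and product are the natural factors there and may be intended for PE too. ANOVA by participant and product separately at each hour is another possible reading. On complete readings its per-hour error was 0 to 5.4%. This stands: the error rates in step 7 belong to particular layouts, not to the plan. The hour-by-hour reading still leaves late-hour selection and multiplicity across hours unaddressed.

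**The stop is not to blame for the error rate.** It is tempting to link the two, but the inflation persists without any stopping. A post-stop rule and a test-level error term are separate repairs. Nor is the stop itself a fault: Section 3.1 defines PE only up to the end of the test, so a mean over all tests had testing continued is a reference introduced here.

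**The loss of a true difference is easily overstated.** Averaging only the readings taken, with hour ignored, reduces 15.8 points to 4.0. Nothing in Section 9.2 commits the analyst to ignoring hour. With hour in the model the loss is about a quarter.

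**PE is secondary.** It carries no stated power or error-rate claim, and the labelling sentence refers to the study's results generally. This limits the weight of the point but does not remove it.

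**Conclusion.** The point holds for the secondary endpoint. Section 9.2 leaves open the factors, the unit of analysis and the post-stop handling, and these choices change the result.

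If tests reach 50% PE before 12 hours at differing times, late hourly means are too high, by roughly 9 to 21 points at hours 6 to 8 in the central illustration (57 − 48 and 35 − 14). A product-and-hour comparison then loses about a quarter of a true difference. This bias is small or nil if products last near or beyond 12 hours. Independently, pooled hourly ANOVA does not generally hold 5%: product and hour ran from under 1% to about 30%, participant and product without hour had almost no power when products fail early, and adding participant to product and hour did not repair it.

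The documents give no PE half-time, spread, decline shape or correlation, so the direction is firmer than the sizes. The primary Kaplan-Meier CPT analysis and its sample size are unaffected. The change should be made before data are seen.

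**What to change.** In Section 9.2:

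1. **Make the test the unit.** Form one PE summary per participant-product test: mean PE over hours 0 to 12, from hourly readings only and not the half-hour confirmatory ones of Section 8.3. Analyse it by two-way ANOVA with factors participant and product, followed by Tukey's comparisons. Label any hourly model exploratory and include participant and participant-by-product effects.
2. **Fix one post-stop rule in advance.** The sponsor chooses it. One example keeps the stopping reading and enters zero at later hours, with last value carried forward as a sensitivity analysis. State that the rule is part of the definition of the summary.
3. **Separate the reasons for ending.** Do not enter zero for a test ended by withdrawal or an adverse event. Keep its data to that point in the analysis, as Section 4.4 requires, say in advance how its summary is formed, and report results with and without such tests. Only random missingness was checked here; product-related endings may be informative.
4. **Keep the hourly table and graph.** Show the number of tests still running at each hour, and mark means after the first stop as coming only from those tests.

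The stopping rule need not change. The cost is wording and a little programming, with no new data. The downsides are real. The summary depends on the chosen rule: for a 6 h half-time, mean PE is 41 to 49 with zero and 57 to 60 carried forward, against 48 in all tests. Carrying forward shrinks the 15.8-point difference to 10.9 (zero gives 15.4). Zero costs power when products last near 12 hours (72% against 88% at half-times 13/13/16 h). Hour-specific tests become exploratory.

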8.5. Follow-up after testing

Participants will be followed up within 72 hours after the test to assess any possible side effects or reactions to the bites and/or products.

9. Statistics and Data Analysis

9.1. Sample size calculation

Using data available from previous arm-in-cage repellent tests using midges, the power was determined for estimation of Complete Protection Times (CPT, primary outcome) at different values and standard deviations (Appendix 4). The sample size was calculated using the sample size formula for the comparison of 2 means with equal standard deviation. The required sample size per group was given by:

$$n = \frac{2\sigma^2}{\delta^2} f(\alpha, \beta)$$

Where δ^2 is the difference between the mean CPTs of 2 treatment groups, σ is the standard deviation of both treatment groups for one comparison which are assumed to be equal. $f(\alpha, \beta) = (z_{1-\alpha/2} + z_{1-\beta})^2$, which varied depending on the specified values of α and β .

9.2. Data analysis

The endpoint for Complete Protection Time will be time to treatment failure for each participant test. Treatment failure is the time at which the product no longer provides complete protection, which is determined as the time at which one probe or bite occurs in a 1 minute test, followed by a confirmatory probe or bite within 30 minutes. Using IBM SPSS Statistics 20, the times to treatment failure will be analysed using Kaplan-Meier Survival functions, and from these the median Complete Protection time and 95% confidence intervals will be calculated.

A linear regression will be used to compare the mean complete-protection time for the tested repellents. As a sensitivity analysis we will use linear regression to estimate the mean CPT difference between groups, but we will generate robust standard errors by relaxing the assumption of independence of observations between the same participant within the study, allowing for correlation between observations from the same participant in the variance-covariance matrix.

The Protective Efficacy over time from application will be calculated using the formula below at each hour and presented as a summary table and graph. Using IBM SPSS Statistics 20, the PE will be analysed using a two-way analysis of variance followed by Tukey's tests or generalised linear model.

$$PE = \frac{\text{Midges probing on control} - \text{Midges probing on treatment}}{\text{Midges probing on control}} \times 100$$

Adverse Events will be tabulated and included in the study report. Adverse events occurring after the end of participant participation but before the end of the study will be listed separately.

10. Safety and Data Monitoring

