Primary/Secondary Objective(s):	
Primary objective: To determine and compare the median complete protection time (CPT) of two insect repellent products and a positive control against Culicoides nubeculosus (midges).
 
Secondary objective: To determine and compare the protective efficacy of two insect repellent products and a positive control against Culicoides nubeculosus (midges).
		
Study Design / Methodology:	A single-centre laboratory setting study using healthy volunteers to test two insect repellent products (NEO-PART prolonged action release technology PMD (40% PMD) And NEO-PART prolonged action release technology PMD (35% PMD)) and a Positive control product (20% Picaridin, 'Smidge') against Culicoides nubeculosus midges.		
Number of Participants:	A total of 7 volunteers will be used to determine the median Complete Protection Time and protective efficacy of two insect repellents and a positive control against one midge species.		
Intended Product Users:	The test products are designed for use by the general public in areas where midge biting is likely.		
Study Duration:	
Participants will undergo a screening evaluation which includes a bite test (monitored for up to 72 hours), followed by up to 3 repellency tests of up to 12 hours duration. Each participant will be followed up after each visit by email/ in person/ by phone within 72 hours of the visit to monitor for adverse events. The minimum interval between the two repellency tests will be 72 hours. The minimum duration of participant involvement would therefore be approximately 3 weeks.
 
Total study duration (recruitment and participant involvement) is anticipated to be 1 month.
		

Inclusion Criteria:
	
 • Able and willing to give fully informed consent; • Able to understand and comply with the study procedures; • Consider themselves to be in good general health; • Male or female; • Aged 18 to 65 years; • Non-smokers or willing to refrain for 12 hours prior to and during each test; • Willing to undergo a bite test with Culicoides nubeculosus midges with up to 72 hour follow-up.

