Appendix 3: Flowchart for Safety Reporting

Appendix 4: Sample Size Calculation for a comparison trial between a positive control and two midge repellent products

A sample size calculation was done using CPT data from a previous study of a repellent against *Culicoides nubeculosus*. The sample size was calculated using the sample size formula for the comparison of 2 means with equal standard deviation. The required sample size per group is given by:

$$n = \frac{2\sigma^2}{\delta^2} f(\alpha, \beta)$$

Where δ^2 is the difference between the mean CPTs of 2 treatment groups, σ is the standard deviation of both treatment groups for one comparison which are assumed to be equal. $f(\alpha, \beta) = (z_{1-\alpha/2} + z_{1-\beta})^2$, which varied depending on the specified values of α and β .

Sample size calculation outcomes

The analysis revealed that for an experiment to compare mean CPT (in min) between any PMD products with Picaridin 20%, assuming a difference in mean CPT of 120 min, with a power of 80% and a significance level of 5%, 7 participants would be required.

A Bonferroni correction was applied for this analysis. The significance level at 5% ($\alpha = 0.05$) was divided by the number of comparisons being made to maintain overall significance level (here divided by 2, as 2 concentrations of PMD are being compared to Picaridin 20%).

Sample size calculation outcomes (with Bonferroni correction) when comparing between two PMD midge repellents and a Picaridin positive control.

Assumption of difference in mean CPT between any PMD group with Picaridin group (minutes)	Number of participants required per arm		
	Alpha = 5% Power = 70%	Alpha = 5% Power = 80%	Alpha = 5% Power = 90%
60	21	26	33
80	12	15	19
100	8	10	12
120	6	7	9
180	3	3	4

If only two arms are compared a Bonferroni correction would not be necessary and the numbers of participants needed for the study are slightly smaller.

Sample size calculation outcomes with the assumption of difference in mean CPT between one midge repellent and a Picaridin positive control.

Assumption of difference in mean CPT between PMD and Picaridin group (minutes)	Number of participants required per arm		
	Alpha = 5% Power = 70%	Alpha = 5% Power = 80%	Alpha = 5% Power = 90%
60	17	21	28
80	10	12	16
100	6	8	10
120	5	6	7
180	2	3	4

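### The main comparison of mean CPT in Section 9.2 treats the 21 results as independent although every participant tests all three products, so with positive within-participant correlation its intervals are too wide and its test conservative

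*Combined protocol and SAP*

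**What the plan says.** - **Design.** Section 3 states: "Each participant will test both PMD formulations and a positive control product (see section 8"). The synopsis sets the number of participants at 7, so a complete study has 7 x 3 = 21 CPT values.
- **Objective.** Section 2 gives the primary objective as "To determine and compare the median complete protection time (CPT) of two insect repellent products and a positive control".
- **Main comparison.** Section 9.2: "A linear regression will be used to compare the mean complete-protection time for the tested repellents". No participant factor, random effect or clustered standard error is named.
- **Sensitivity analysis.** The next sentence of Section 9.2 keeps linear regression, but "we will generate robust standard errors by relaxing the assumption of independence of observations between the same participant within the study". It gives no small-sample correction and no reference distribution.
- **Synopsis, Statistical Methods.** The CPT model is worded differently: "Two-way analysis of variance followed by Tukey's tests or general linear mode will be used to compare the mean complete-protection time". The two factors are not named. In Section 9.2, two-way analysis of variance appears only for Protective Efficacy.
- **Sample size.** Appendix 4 uses the formula for two independent means and reaches 7 participants for a 120 min difference at 80% power. On multiplicity it says "A Bonferroni correction was applied for this analysis", with 5% divided by 2.

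**The concern.** Section 9.2 describes its sensitivity analysis as the one that drops independence within a participant, so independence is an assumption of the main analysis. That does not fit a design in which each participant serves as his or her own control.

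The direction matters. When whole clusters receive one treatment, ignoring clustering makes standard errors too small. Here products are compared within participants, so differences between people cancel from each product contrast. A model that leaves those differences in the residual gives standard errors that are too large whenever rho is positive.

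This regression and its sensitivity version are the only between-product comparisons of CPT in Section 9.2. With 7 participants there is little precision to spare, and Section 3.2.2 says that the results will inform product labelling.

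**Working it through.** **Inputs**

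- n = 7 participants and 3 products (synopsis, Section 3).
- Planned difference 120 min, power 80%, alpha 0.05/2 = 0.025, two-sided (Appendix 4).
- SD of CPT: not stated, so back-solved below.
- rho: not stated, so shown over a range.

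**1. Reproduce the plan's figure.** Appendix 4 uses n = 2 x SD^2 x f / delta^2, with f = (z at 1-alpha/2 + z at power)^2. Any SD from 68.81 to 68.98 min, with rounding up, reproduces all 30 cells of the two tables (alpha 0.025 in the Bonferroni table, 0.05 in the other). With SD 68.9, f = (2.241 + 0.842)^2 = 9.505 and n = 2 x 68.9^2 x 9.505 / 120^2 = 6.27, rounded up to 7. This matches the plan. Because the SD is fitted, the agreement confirms the formula, not the SD.

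**2. Standard error of a product difference.**

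- What the plain regression estimates: SD x sqrt(2/n) = 68.9 x sqrt(2/7) = 36.8 min, whatever rho is.
- The true value: SD x sqrt(2(1-rho)/n) = 36.8 min at rho 0, 30.8 at 0.3 and 26.0 at 0.5.
- Ratio 1/sqrt(1-rho): 1.00, 1.20 and 1.41.

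With complete data the estimated differences are the same with or without a participant effect. Residual degrees of freedom are 21 - 3 = 18 without it and 21 - 3 - 6 = 12 with it.

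**3. Intervals, size and power.** These come from at least 100,000 simulated 7 x 3 data sets per setting (normal, uncensored, equal correlation, SD 68.9). Power for the participant model was checked against the exact noncentral t. Pairs are plain regression v participant model.

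| rho | Mean 95% half-width (min) | True size of plain test at nominal 5% | Power at 120 min, alpha 0.025 | Power at 100 min, alpha 0.025 |
|---|---|---|---|---|
| 0 | 76 v 79 | 5.0% | 78% v 75% | 61% v 57% |
| 0.3 | 76 v 66 | 2.3% | 82% v 89% | 63% v 74% |
| 0.5 | 76 v 56 | 1.1% | 84% v 97% | 65% v 88% |

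The participant model holds its size at about 5% throughout. At 120 min the two models have equal power at rho of about 0.1 (79.4% v 79.5%).

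**4. The sensitivity analysis with 7 clusters.** The uncorrected cluster-robust standard error of a difference is the paired-t standard error times sqrt(6/7). The standard correction multiplies the variance by (7/6) x (20/18), which makes it the paired-t standard error times sqrt(20/18) = 1.054. The paired t statistic has 6 df at any rho, so true size at nominal 5% does not depend on rho:

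- uncorrected, normal reference: critical |t| = 1.96 x 0.926 = 1.81, size about 12%;
- standard correction, normal reference: 1.96 x 1.054 = 2.07, size about 8%;
- standard correction, t with 6 df: 2.447 x 1.054 = 2.58, size about 4%.

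**The case against.** The strongest reply has four parts.

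- **A correlation-adjusted analysis is already planned.** This is true, and the estimates will agree, so the issue is which analysis leads. It does not settle the matter: the adjusted analysis is secondary, and its error rate ranges from about 4% to 12% depending on choices that Section 9.2 leaves open. The two higher figures arise only with a normal reference, which the section neither states nor rules out.
- **The synopsis may already hold the remedy.** With one CPT per participant per product, participant is the natural second factor of a two-way analysis of variance. That reading is fair, but the factor is not named and Section 9.2 says something else. The two places need reconciling in any case.
- **Planned power is roughly met.** Appendix 4 wants 80% at 120 min, and the plain regression gives 78% at rho 0, 82% at 0.3 and 84% at 0.5. This stands. At 120 min the cost is forgone extra power, not a shortfall caused by ignoring the matching. The loss is larger at 100 min, a difference for which n was not chosen.
- **Size depends on alpha, rho and the data model.** Section 9.2 sets no multiplicity rule for the regression. At alpha 0.05 and 120 min the power figures are 87% v 85% (rho 0), 90% v 95% (0.3) and 93% v 99% (0.5), so the gap narrows. With CPT rounded to hourly tests, power at alpha 0.025 is 79% v 86% at rho 0.3 and 81% v 95% at 0.5: the same direction at slightly lower levels. Censoring at 12 hours was not modelled.

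**Conclusion.** The concern holds. As written, the main comparison of mean CPT assumes independence in a fully crossed design. If rho is positive, its intervals are too wide and its test conservative: at rho 0.5 the standard error is about 41% too large and the 95% interval about 36% wider than needed. It does not bias the estimates, create false-positive claims or affect the Kaplan-Meier medians, which do not come from this model.

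The figures rest on complete, normal, uncensored CPTs with equal correlation, an SD inferred from Appendix 4, and a rho that the documents do not give. If rho is 0 the main analysis loses nothing. It should be fixed because the change is nearly free and the study is small, not because planned power at 120 min is lost.

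**What to change.** 1. In Section 9.2, make the main comparison of mean CPT a model with product and participant effects: two-way analysis of variance, or a mixed model with a random participant effect, with 12 residual df for product differences.
2. Word the synopsis the same way and name participant as the second factor.
3. Keep the cluster-robust regression as the sensitivity analysis, and state that it uses a small-sample correction and t with 6 df.

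**Cost.** Wording only; data collection and sample size do not change. There are three downsides:

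- If rho is 0, power at 120 min and alpha 0.025 falls by about 4 points (78.4% to 74.8%). The participant effect gains power only above rho of about 0.1.
- The participant model assumes equal variances of the pairwise product differences. The retained cluster-robust analysis does not.
- The corrected cluster-robust analysis has less power at 120 min and alpha 0.025 (58%, 75% and 88% at rho 0, 0.3 and 0.5), so it suits the sensitivity role rather than the main test.
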